In the TFLs, subjects randomized to BKZ 160mg Q4W will be labeled as “BKZ 160mg Q4W”, subjects randomized to ADA 40mg Q2W will be labeled as “ADA 40mg Q2W” and subjects randomized to Placebo will be labeled as “Placebo / BKZ 160mg Q4W” (or “Placebo” when the TFLs report data from the DBP only).

For the ATP, all subjects on BKZ 160mg Q4W (that includes the subjects switching from Placebo at Week 16) will be labeled as “BKZ 160mg Q4W Total” in the TFLs.

Per protocol, visit windows of ± 2 days from the first dose at all visits through Week 16 and ± 3 days after Week 16 are permissible. For the SFU visit, the visit should occur no more than 3 days prior to the scheduled visit date and within 7 days after the scheduled visit date.

For the medical imaging collection date (at Week 16 and 52), the allowed visit window will be extended to ± 14 days around the scheduled visit date.

All by-visit tables will contain nominal (ie scheduled) visits only. Unscheduled visits will not be mapped to scheduled visits except for some assessments that may occur within the above visit window of a scheduled visit. In that case, the assessment will be mapped to the corresponding scheduled visit and will be used for the analysis unless data are present for that scheduled visit. Only data collected/mapped at the scheduled visits will be included in the analysis. The only deviation may concern unscheduled vendor data collected ([Section 10.5](#)).

Assessments collected at unscheduled and repeated visits will only be listed, except in the case of determining treatment-emergent markedly abnormal criteria for laboratory and vital sign parameters where all post-Baseline (scheduled and unscheduled) values will be used.

For by-visit tables summarizing efficacy data, the SFU visit will not be included but SFU efficacy data will be listed. By-visit tables summarizing safety data will however include the SFU visit. For PK, immunological and immunogenicity analyses, SFU data will be part of the data reported in some tables ([Section 9](#)).

A complete set of data listings containing all documented data and all derived data (eg, change from Baseline) will be generated.

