Unless otherwise stated, listings will be sorted by treatment group, subject number within each treatment group (not randomization number), variable (if applicable) and visit (if applicable, including timing relative to dosing if applicable). For listings including non-randomized subjects, the non-randomized subjects will be shown first in the listing, ordered by subject number. All listings will include repeated and unscheduled measurements. Such measurements will appear in chronological order together with the scheduled visits (ie: a repeated measurement will appear directly after the visit and time relative to dosing for which the repeat measurement was performed). In all the listings dates will be presented in the format ‘YYYY-MM-DD’ and times will be presented in 24h clock format as ‘hh:mm’.

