10.2.4.8 Hepatic events and DILI

A table for hepatic events will be created based on the SMQ of "Drug related hepatic disorders - comprehensive search (SMQ)". However, these 2 sub-SMQs are to be excluded: "Liver

neoplasms, benign (incl. cysts and polyps) (SMQ)” and “Liver neoplasms, malignant and unspecified (SMQ) “. For each of the above SMQs, include all TEAEs which code to a PT included in the Scope=Broad and/or Scope=Narrow.

Note that all AEs meeting the above criteria are to be included. It should not be limited to events that the investigator determined to be related to study drug.

Potential cases of Hy’s Law will be reported separately in a liver function test table ([Section 10.3](#)).

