Parameter name	Unit	Criteria	Abnormal designation
Creatinine	mmol/L	>3.0 x ULN or >3.0 x Baseline	AH
Glucose	mmol/L	<2.2 >13.9	AL AH
Calcium	mmol/L	>3.1 <1.75	AH AL
Magnesium	mmol/L	>1.23 <0.4	AH AL

Parameter name	Unit	Criteria	Abnormal designation
Potassium	mmol/L	>6.0	AH
		<3.0	AL
Sodium	mmol/L	>155	AH
		<130	AL
Triglyceride	mmol/L	>5.7	AH
Cholesterol	mmol/L	>10.34	AH

AH=abnormal high; AL=abnormal low; dL = deciliter; L = liter; mg = milligram; mmol = millimoles; ULN = upper limit of normal.

Table 10–4: Definitions of markedly abnormal hematology values

Parameter name	Unit	Criteria	Abnormal designation
Hemoglobin	g/L	<80	AL
		>40 above ULN or >40 above Baseline if Baseline is above ULN	AH
Lymphocytes Absolute	$10^9/L$	<0.5	AL
		>20.0	AH
Neutrophils Absolute	$10^9/L$	<1.0	AL
Platelets	$10^9/L$	<50	AL
WBC/ Leukocytes	$10^9/L$	<2.0	AL
		>100	AH

Table 10–5: Definitions of markedly abnormal liver enzyme elevation values

Parameter name	Unit	Criteria	Abnormal designation
Alkaline Phosphatase		>5.0 x ULN	AH
ALT	U/L	>5.0 x ULN	AH
AST	U/L	>5.0 x ULN	AH
Total Bilirubin	umol/L	>3.0 x ULN	AH
GGT	U/L	>5.0 x ULN	AH

ALT= alanine aminotransferase; AST = aspartate aminotransferase; GGT= gamma-glutamyltransferase

Definitions of the markedly abnormal values for liver enzyme elevation are given in [Table 10–5](#).

All laboratory summaries will be presented in standard international (SI) units and will be based on observed case values. In the case where laboratory values are below the LLOQ, then these will be set to the midpoint between 0 and the LLOQ for the purpose of summarizing the data.

In the case where laboratory data are expressed as above a fixed value (ie, “>xx.xx”), then the numeric portion of the value will be used (ie, xx.xx) to present and calculate statistics.

To define the minimum/maximum post-Baseline values, all post-Baseline assessments including those at unscheduled visits (but excluding any that occur more than 140 days after the last administration of study medication) will be used.

The following additional rule will be also applied :

Subjects who have completed PA0010 and have a PA0012 start date, only PA0010 results up to and including the PA0012 start date will be used to find the subjects minimum or maximum results. Additionally, subjects who are in PA0012 without a start date (date of first dose), only PA0010 results up to the Week 52 visit + 14 days will be used to find the subjects minimum or maximum results.

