Different summary tables for hematology, biochemistry variables (except hs-CRP which will be analyzed in the efficacy section) and urinalysis (pH, Albumin (protein), glucose, blood, leukocyte esterase and nitrite) will be provided in the SS. For shift tables, results for the DBP and the ATP will be presented together for the overall study period.

As indicated in [Section 3.1](#), for tables where data are summarized by visit only values occurring at scheduled visits will be included.

For each laboratory parameter, the below results will be presented for the overall study period, by treatment (Placebo/BKZ 160mg Q4W, BKZ 160mg Q4W and ADA 40mg Q2W):

- Observed values at Baseline and observed values and changes from Baseline at each scheduled post-Baseline visit
- Number and percentage of subjects by CTCAE grade (version 4.03) (when applicable) based on minimum/maximum post Baseline value (for blood chemistry and hematology). Subjects who meet the decreased potassium criterion of $3.0 < \text{LLN}$, which is specified as the decreased potassium lab criterion for both CTCAE Grade 1 and Grade 2, will be counted as Grade 2.
- Shift in CTCAE grade from Baseline to minimum/maximum post-Baseline value (for blood chemistry and hematology)
- Number and percentage of subjects meeting the below criteria at any time during the study:
 - AST: $>2 \times \text{ULN}$, $>3 \times \text{ULN}$, $>5 \times \text{ULN}$, $>10 \times \text{ULN}$, $>20 \times \text{ULN}$
 - ALT: $>2 \times \text{ULN}$, $>3 \times \text{ULN}$, $>5 \times \text{ULN}$, $>10 \times \text{ULN}$, $>20 \times \text{ULN}$
 - AST or ALT: $>2 \times \text{ULN}$, $>3 \times \text{ULN}$, $>5 \times \text{ULN}$, $>10 \times \text{ULN}$, $>20 \times \text{ULN}$
 - Bilirubin: $>1 \times \text{ULN}$, $>1.5 \times \text{ULN}$
 - ALP: $>2 \times \text{ULN}$
- Number and percentage of subjects with potential Hy's Law cases based on the 2 following definitions:
 - $[\text{AST} \geq 3 \times \text{ULN} \text{ or } \text{ALT} \geq 3 \times \text{ULN}] \text{ and Total Bilirubin} \geq 2 \times \text{ULN}$
 - $[\text{AST} \geq 3 \times \text{ULN} \text{ or } \text{ALT} \geq 3 \times \text{ULN}] \text{ and Total Bilirubin} \geq 2 \times \text{ULN}$ in the absence of $\text{ALP} \geq 2 \times \text{ULN}$

To meet either of the above criteria, a subject must experience the elevation in bilirubin and ALT or AST (and the absence of ALP elevation, if applicable) at the same visit.

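### Section 3.1's listing-only rule for unscheduled results contradicts Section 10.3's minimum/maximum rule and any-time liver counts, and leaves the potential Hy's Law count without a clear rule

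*SAP*

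**What the plan says.** Section 3.1 opens the relevant paragraph with by-visit tables, which are to show scheduled visits only. It then widens: "Only data collected/mapped at the scheduled visits will be included in the analysis". An unscheduled result that falls inside a visit window is mapped to that visit, but it "will be used for the analysis unless data are present for that scheduled visit". The next paragraph gives the general rule: "Assessments collected at unscheduled and repeated visits will only be listed, except in the case of determining treatment-emergent markedly abnormal criteria", the exception being for laboratory and vital sign parameters. Possible deviation is also allowed for unscheduled vendor data, with a reference to Section 10.5. Listings are complete: "All listings will include repeated and unscheduled measurements".

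Section 10.3 treats laboratory outputs as follows.

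- Minimum and maximum post-Baseline values use "all post-Baseline assessments including those at unscheduled visits", "excluding any that occur more than 140 days after the last administration of study medication". These values feed the CTCAE grade counts and the CTCAE shift tables.
- The AST, ALT, bilirubin and ALP threshold counts are headed "Number and percentage of subjects meeting the below criteria at any time during the study".
- The potential Hy's Law count is a separate bullet. It requires the elevations to occur at the same visit and does not mention unscheduled samples.
- A sentence admitting scheduled and unscheduled values comes after the Hy's Law bullet and applies to the tables below it, which are the two markedly abnormal tables.
- Just above the bullets, Section 10.3 refers back to Section 3.1 and describes it as restricting tables summarized by visit.

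Section 10.2.4.8 says that potential Hy's Law cases "will be reported separately in a liver function test table", and points to Section 10.3.

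**The concern.** A general rule and a specific section give different answers about which samples count. For the CTCAE tables and the liver-threshold rows, Section 10.3 says enough to show what is intended, but it contradicts Section 3.1 in doing so. For the Hy's Law count, Section 10.3 does not say which samples enter, and two careful programmers could build different filters from the same text.

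This matters because abnormal liver tests are commonly followed by repeat or extra samples, and those are what Section 3.1 sends to the listings. The Hy's Law output is a rare-event safety count in which a single subject is informative. It is also the only planned table in which ALT/AST and bilirubin are looked at together.

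**Working it through.** There is no planned figure to reproduce. The check is textual, with one threshold comparison and one simple proportion.

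**Step 1: how far Section 3.1 reaches.** The paragraph starts with by-visit tables, so it could be a by-visit rule only. Against that, the listing-only sentence needs an exception for markedly abnormal laboratory and vital sign values. In Section 10.3 those laboratory outputs are overall counts and not by-visit summaries. If the rule reached by-visit tables alone, the exception would be unnecessary. As written, the rule therefore reaches overall counts. The sentence carries no qualifier deferring to other sections.

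**Step 2: Section 3.1 against Section 10.3, output by output.**

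| Output in Section 10.3 | Section 3.1 read literally | Section 10.3 | Result |
|---|---|---|---|
| CTCAE grade and shift, from minimum/maximum | Not in the exception: scheduled or mapped values only | Unscheduled values included, to 140 days after last dose | Explicit contradiction |
| AST/ALT/bilirubin/ALP thresholds | Not in the exception | Counted over the whole study | Contradiction on the plain meaning |
| Potential Hy's Law | Not in the exception | No inclusion sentence; by-visit paraphrase of 3.1 stands above it | Two readings available |
| Markedly abnormal laboratory values and liver enzymes | In the exception | Unscheduled values included | Consistent |

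**Step 3: does in-window mapping rescue the repeat sample?** Only when the scheduled visit has no result. A repeat liver test taken beside a scheduled one stays in the listings, and so does an unscheduled sample outside every window.

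**Step 4: is there another table that would catch the case?** Take ALT 4xULN with bilirubin 2.5xULN on one unscheduled sample.

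- Hy's Law, first definition: ALT or AST at least 3xULN (4 ≥ 3, met) and total bilirubin at least 2xULN (2.5 ≥ 2, met). The second definition is also met if ALP is below 2xULN.
- Table 10-5: ALT or AST above 5xULN (4 > 5, not met); bilirubin above 3xULN (2.5 > 3, not met).
- The CTCAE maxima can show each parameter separately, and so can the threshold rows if their any-time wording is followed (ALT above 3xULN, bilirubin above 1.5xULN). They are marginal counts, and a same-visit joint count cannot be rebuilt from them.

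So under a literal Section 3.1 this subject appears in the listings and possibly in single-parameter rows, but in no joint count.

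**Step 5: what one subject is worth.** At the planned arm sizes in Section 2.3.1:

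- BKZ: 1/420 = 0.24%
- Placebo/BKZ: 1/280 = 0.36%
- ADA: 1/140 = 0.71%

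**The case against.** The strongest reply is that Section 10.3 itself says what Section 3.1 means for laboratory data: the scheduled-only restriction is for by-visit tables. The Hy's Law output is a per-subject count over the study and not a by-visit table. Other sections point the same way. Section 9.2.1 uses scheduled and unscheduled data for all antibody summaries that are not by visit, and Section 10.2.5 bases interim safety tables on all data available at the snapshot. The same-visit condition asks for concurrence and does not say the visit must be scheduled. A programmer who admits unscheduled samples to the threshold rows has little reason to exclude them from the next bullet. All laboratory values are listed, hepatic events are also tabulated and listed, and no efficacy inference is touched. The table shells might settle the matter, but they are not part of the document.

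Most of this stands. It means exclusion from the Hy's Law count is one available reading and not a certainty. It does not remove the contradiction. Section 3.1's own wording goes beyond by-visit tables (step 1), the plan does not say which section prevails, and no sentence brings unscheduled samples into the Hy's Law count.

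A reader might infer that the plan definitely drops unscheduled samples from the Hy's Law table, or that it hides such cases. The documents support neither: Section 10.3's paraphrase allows the inclusive reading, and the values are listed in full. A reader might also try to size the loss by the share of study days outside every visit window. That does not measure missed cases, because liver tests are not spread evenly over days and the plan gives no share of unscheduled samples.

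**Conclusion.** Wrong as written, as an internal contradiction, and of minor severity. Section 3.1's listing-only rule is explicitly contradicted by Section 10.3's minimum/maximum rule, and on plain meaning by its any-time liver-threshold counts. For potential Hy's Law cases the plan supports two readings. Under the literal one, a joint elevation found only on an unscheduled or repeat sample is missing from the one table designed to count it, and Table 10-5 is no backstop at moderate multiples of the ULN.

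The size of any undercount is unknown. The percentages for one subject assume the planned arm sizes and say only how a column would move, not how likely that is. The output is descriptive, and the individual values remain visible in the listings.

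**What to change.** In Section 3.1, either limit the scheduled-only and listing-only rule to by-visit tables, or extend the exception to the minimum/maximum (CTCAE), liver-threshold and Hy's Law outputs.

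In Section 10.3, state that the liver-threshold and Hy's Law counts both use all post-Baseline values, scheduled and unscheduled, up to 140 days after the last dose. That is the cut-off already set for minimum and maximum values. Define same visit, for the Hy's Law condition, as the same sample date, so that unscheduled and repeat samples can be classified.

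The cost is a few lines of SAP text and a programming filter. The data are already collected and listed.

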3.2 General study level definitions

3.2.1 Relative day

The relative day will be included in some listings. The way that relative day is calculated depends on when the given event occurs relative to the date of first IMP administration.

- If the event occurred on or after the date of first IMP administration (but before the last IMP administration), then the following calculation is used: Relative Day=Date of event - Date of first IMP administration + 1.
- If the event occurred before the date of first IMP administration, then the following calculation is used: Relative Day=Date of event - Date of first IMP administration. Relative days that occur before the date of first IMP administration should be preceded by a “-”.
- If the event occurred after the date of last IMP administration, then the following calculation is used: Relative Day=Date of event - Date of last IMP administration. Relative days that occur after the date of last IMP administration should be preceded by a “+”.

Relative day will only be computed for fully completed dates and will be missing for partial dates.

For AEs, relative days for start and stop dates will be calculated as the number of days since the date of first IMP administration.

For subjects in the placebo group that switch to BKZ at Week 16, for events occurring after Week 16, an additional relative day will be calculated using the same rules as above but based on the date of first injection of BKZ. This additional relative day will be provided in listings for concomitant medications and safety data.

For non-treatment-emergent AEs, relative day of onset will be negative if the event started before the date of first IMP administration. A complete date must be established to correctly identify the AEs. [Section 4.2.3](#) describes imputation rules in case of missing data for AEs.

3.2.2 Mapping of assessments performed at Early Discontinuation Visit

Study assessments at an early termination visit where visit date matches the visit date of a scheduled visit will be summarized at the scheduled visit with the same visit date. Premature study termination visit assessments that do not have a scheduled visit with a matching date will be assigned a visit based on the protocol-defined visit windows (± 2 days up to and including Week 16, and ± 3 days from Week 20 up to and including Week 52). For early discontinuation visits that fall between protocol defined visit windows and not within them, the later of the 2 visits is assigned.

If there is an existing scheduled site visit in the window, then the assessments at the ET visit will be mapped to the next scheduled site visit.

The ADAb assessments, PK and the vdHmTSS are exceptions to this rule:

- ADAb levels, PK from an early termination visit will be mapped to the next visit where they are measured.

- VdHmTSS from an early termination visit will be mapped to the Week 16 assessment (if the early termination is before Week 16) or to the Week 52 assessment (if the early termination is between Week 16 and Week 52).

3.3 Definition of Baseline values

A Baseline value for a subject is defined as the latest measurement for that subject up to and including the day of first administration of IMP (Visit 2 by default), unless otherwise stated.

By default, for randomized subjects for whom no start date of treatment is available, the Baseline value will be considered as the last available value prior to the randomization date.

If a Baseline assessment is taken on the same day as first administration of IMP, it is eligible to be used as the Baseline value, even in the case that the time of the assessment is recorded as taking place after the time of first administration of IMP. This is considered acceptable as this measurement is still the best representation of the Baseline value of the given assessment since it is highly unlikely that the IMP could have an impact on any measurement in such a short period of time. However, such cases should be rare as study center personnel are instructed to do all assessments at the Baseline visit prior to administering IMP. One exception to this rule is plasma concentration. If Baseline plasma concentration is measured at a time after the first administration of IMP, then it should not be eligible to be considered as a Baseline plasma concentration. Such cases should be discussed with the quantitative clinical pharmacologist.

If a Baseline measurement is missing or not collected, and a Screening value is available, the Screening value will be utilized as Baseline instead. If no measurement is available prior to receiving IMP, then the Baseline value is treated as missing.

Baseline values for component scores should be computed using components from the same visit where the relevant measurements were recorded prior to dosing. For example, if the Screening visit has all the components, but the Baseline visit is missing one or more components, the Baseline value for the component score should be calculated using the Screening visit values.

When the time of first dose is derived, it should be based on the first injection of IMP, regardless of whether it is an active treatment.

Chest x-ray performed within 3 months before the Screening visit is considered as Baseline measurement.

For subjects who switch treatment from placebo to BKZ at Week 16 (Visit 10), an additional Baseline value (called Week 16 Baseline) will be defined for efficacy variables. The Week 16 value will be considered as the Baseline value regardless of whether the Placebo subjects switched to BKZ on a later visit.

The variables listed below will be analyzed relative to the Week 16 Baseline value for the ATP, for timepoints after Week 16:

- PASI90 response
- ACR50 response.

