10.4 Vital signs, physical examination findings, and other observations related to safety

10.4.1 Vital signs and physical examination findings

The vital signs (systolic BP (mmHg), diastolic BP (mmHg), and pulse rate (beats/min)) will be summarized as:

- Absolute and change from Baseline at each scheduled visit on the SS for the full study period by randomized treatment
- For systolic and diastolic blood pressure, number and percentage of subjects experiencing at least one markedly abnormal value as defined in [Table 10-6](#).

Table 10-6: Definitions of markedly abnormal blood pressure values

Parameter (unit)	Markedly abnormal low	Markedly abnormal high
Systolic blood pressure (mmHg)	<90 and a decrease from Baseline of ≥ 20	>180 and an increase from Baseline of ≥ 20

Parameter (unit)	Markedly abnormal low	Markedly abnormal high
Diastolic blood pressure (mmHg)	<50 and a decrease from Baseline of ≥ 15	>105 and an increase from Baseline of ≥ 15

For the Baseline visit where several BP assessments are taken, the individual observed data assessments as well as the mean of these assessments will be summarized and listed (pre-dose, 30 min post-dose and 1-hour post-dose).

Treatment-emergent markedly abnormal values will be analyzed on the SS (for the DBP, by treatment), on the ATS (for the ATP by treatment and for all BKZ-treated subjects), and on the AMS (for all BKZ-treated subjects and the ADA group).

Vital signs measurements will also be listed by visit and timing relative to dosing including changes from Baseline. The listing will also include details of abnormal value based on flags as defined in [Table 10-6](#) ("L" for markedly abnormal low and "H" for markedly abnormal high).

Similarly, physical examination findings together with the details of abnormalities (when applicable) will be listed by treatment group, subject and visit.

Body weight will be only listed.

10.4.2 **Electrocardiograms**

The following ECG variables will be assessed at Baseline (Screening visit), Week 16, Week 52 and at the end of SFU:

- Heart Rate (bpm)
- PR interval (ms)
- RR interval (ms)
- QRS duration (ms)
- QT interval (ms)
- QTcF interval (ms)
- QTcB interval (ms)

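### Read literally, the Baseline rule makes the 1-hour post-dose blood pressure the Baseline, so post-dose shifts on Day 1 cannot be flagged and later changes use a post-dose reference

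*SAP*

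**What the plan says.** SAP Section 3.3 gives one general rule. Unless stated otherwise, Baseline is "defined as the latest measurement for that subject up to and including the day of first administration of IMP". A reading on that day is eligible "even in the case that the time of the assessment is recorded as taking place after the time of first administration of IMP". The section gives two reasons: the drug is unlikely to act so quickly, and "such cases should be rare as study center personnel are instructed to do all assessments at the Baseline visit prior to administering IMP". One variable is carved out: "One exception to this rule is plasma concentration". Vital signs are not. Later in the same section: "If no measurement is available prior to receiving IMP, then the Baseline value is treated as missing".

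Section 10.4.1 shows that several blood pressure readings are taken at the Baseline visit. The individual values and the "mean of these assessments will be summarized and listed (pre-dose, 30 min post-dose and 1-hour post-dose") are to be reported. It does not say which of them is the Baseline for change from Baseline or for Table 10-6.

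Table 10-6 combines an absolute limit with a change. The low systolic criterion is "<90 and a decrease from Baseline of" at least 20 mmHg, and the other three are built the same way. Section 3.1 says which values are assessed: "determining treatment-emergent markedly abnormal criteria for laboratory and vital sign parameters where all post-Baseline (scheduled and unscheduled) values will be used".

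**The concern.** Section 3.3 defends post-dose Baselines as rare accidents of timing. For blood pressure they are planned: two of the three Baseline-visit readings follow the injection by design. With no vital-signs exception and nothing stated otherwise in Section 10.4.1, taking the latest same-day value leads to the 1-hour reading.

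A Baseline is meant to be the untreated reference. If a subject's pressure falls or rises after the first injection, this rule puts the shift into the reference. The shift then disappears from that subject's Day 1 changes and carries over, with the opposite sign, into every later change. The outputs at stake are the blood pressure change-from-Baseline summaries and the table of markedly abnormal values, in all three arms.

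The claim that the drug cannot act so soon also sits badly with the rest of the plan. Section 10.2.4.7 and Appendix 1 search for acute anaphylaxis on the injection day or the day after, with hypotension terms in the algorithm. Section 10.2 assigns hypersensitivity events on the day of the switch to bimekizumab.

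**Working it through.** The plan gives no figure to reproduce, so the check applies its rules to example readings.

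**Inputs from the SAP**
- Baseline: latest value through the day of first dose, with same-day post-dose values eligible (Section 3.3).
- Day 1 readings: pre-dose, 30 minutes and 1 hour after dosing (Section 10.4.1).
- Systolic criteria: below 90 with a fall of at least 20, or above 180 with a rise of at least 20 (Table 10-6).
- Diastolic criteria: below 50 with a fall of at least 15, or above 105 with a rise of at least 15 (Table 10-6).
- Values assessed: post-Baseline only (Section 3.1).

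**Assumed:** all blood pressure readings below.

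**Step 1: which reading is Baseline.** Of the three Day 1 readings, the latest is the 1-hour value. It falls on the day of first dose, is eligible although post-dose, and is not plasma concentration. The sentence that treats Baseline as missing when there is no pre-dose value does not change the selection: once a pre-dose value exists its condition is not met, and the latest-value rule still picks the 1-hour reading.

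**Step 2: Day 1 flags.** Change = reading − Baseline.

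| Assumed pre / 30 min / 1 h | Reading | Change from pre-dose | Flag | Change from 1-hour Baseline | Flag |
|---|---|---|---|---|---|
| SBP 112 / 98 / 86 | 86 (1 h) | 86 − 112 = −26 | low | 86 − 86 = 0 | none |
| SBP 150 / 190 / 190 | 190 (1 h) | 190 − 150 = +40 | high | 0 | none |
| DBP 75 / 45 / 45 | 45 (1 h) | 45 − 75 = −30 | low | 0 | none |
| DBP 85 / 110 / 110 | 110 (1 h) | 110 − 85 = +25 | high | 0 | none |
| SBP 120 / 85 / 100 | 85 (30 min) | 85 − 120 = −35 | low | 85 − 100 = −15, taken before Baseline | none |

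The 1-hour reading always has zero change from itself. The 30-minute reading precedes it, so it is not a post-Baseline value and is not assessed.

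**Step 3: later visits.** Let d = 1-hour reading − pre-dose reading. A later value Y has change Y − (pre-dose + d) = (Y − pre-dose) − d, so each later change is off by −d.
- Missed flag: readings 112 / 98 / 86 give d = −26. A Week 2 value of 88 is 88 − 112 = −24 from pre-dose (flagged), but 88 − 86 = +2 from the 1-hour Baseline (not flagged).
- Spurious flag: pre-dose 170 and 1-hour 150 give d = −20. A later 182 is 182 − 170 = +12 from pre-dose (not flagged), but 182 − 150 = +32 from the 1-hour Baseline (flagged).

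The error can therefore go either way.

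**The case against.** The best defence is that the text does not settle on the 1-hour reading. The rule yields to anything stated otherwise. A same-day post-dose value is only eligible, and that paragraph is about Baseline assessments that happened to run late, not readings scheduled as post-dose. The sentence on missing Baselines implies a pre-dose value. Section 10.4.1 plans a listing by timing relative to dosing with changes from Baseline, which makes most sense against the pre-dose reading.

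This shows that a pre-dose Baseline may be what was meant, and part of it stands: Section 3.3 pulls two ways. But no sentence names the pre-dose reading as Baseline, and the operative definition asks for the latest value. Two programmers could derive different Baselines from this text.

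Three stronger readings are tempting, and the document does not support them.
- **That the three-reading mean is the Baseline.** Section 10.4.1 only summarizes and lists it. Even if it were the reference, flags would be attenuated, not impossible. If both post-dose readings shift by d, the change from the mean is d/3, so d must reach 60 mmHg systolic or 45 diastolic. Assumed readings of 150 / 85 / 85 have mean 106.7 and change −21.7, which would meet the low systolic criterion if Day 1 values were tested.
- **That the safety reporting is blind to acute changes.** Each Day 1 reading is summarized and listed. Section 10.2.1 lists adverse events at first administration, and the anaphylaxis table covers the injection day and the day after.
- **That these readings cover the period of highest risk.** The SAP says this nowhere.

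**Conclusion.** The point holds as a poorly fixed derivation. Applied literally, Section 3.3 gives blood pressure a post-dose Baseline, and its reason for tolerating such Baselines fails for a variable measured after dosing by plan. Day 1 post-dose readings then cannot be flagged under Table 10-6, and later changes and flags use a post-injection reference.

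The rule reaches every treated subject, about 840 as planned, and a reader might take that as the number affected. It is not: only a subject whose pressure moved between the pre-dose and 1-hour readings can be misclassified, and the SAP gives no basis for estimating how many. The damage is confined to the change-from-Baseline blood pressure summaries, the markedly abnormal table and the listing flags. No efficacy result, hypothesis test or error rate is touched. The correction should be made because these are safety tables and the repair is easy.

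The conclusion rests on the literal reading of Section 3.3 and on nothing in Section 10.4.1 overriding it. The example readings are assumptions; the thresholds are the SAP's.

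**What to change.** - **Section 3.3:** add vital signs to the exception now limited to plasma concentration, so that Baseline is the last value before the first injection. Reconcile the same-day rule with the sentence on missing Baselines.
- **Section 10.4.1:** repeat that definition for blood pressure. State that the 30-minute and 1-hour readings are post-Baseline and enter the Table 10-6 assessment. Label the mean of the Day 1 readings as descriptive only and not the Baseline.

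The cost is a few sentences and one change to the derivation of the vital-signs dataset. All three readings are already collected, so no new data are needed.
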